A 2007 study by Narayanaswamy et al. demonstrated a difference between the generic and original versions of Latanoprost. This pilot study involving 30 patients in a single center in India seemed to demonstrate that generic Latanoprost was less effective than Xalatan in lowering IOP. [8]. However, this is only a small study and some questions about the reliability of the results have surfaced, including concerns regarding the improper storage of the generic Latanoprost used.

On the other hand, several studies have shown an equivalence between the generic drug and the original. A randomized, double-blind study in 2011 by Diguini et al., involving 184 patients, demonstrated the non-inferiority of a generic version of Latanoprost compared to Xalatan.[9]. On the other hand, the generic version used in this study had a composition qualitatively and quantitatively identical to Xalatan, which is often not the case [4][10]. Another randomized multicentre study, by Allaire et al., included 266 patients with diagnosis of primary open angle glaucoma and ocular hypertension. Each patient was assigned to the generic Latanoprost group or the Xalatan group in a ratio of 1: 1. This study demonstrated therapeutic equivalence as well as the same safety profile [11]. Finally, a randomized crossover study by Golan et al. in 2015, compared Glautan, a generic version of Latanoprost, to Xalatan in 19 patients. The hypotensive effect and ocular side effect profile was comparable [12].

2. Objectives

The primary goal was to determine if generic Sandoz-Travoprost is as effective as brand Travatan Z in lowering intraocular pressure, as measured using Goldmann applanation tonometry.

The secondary goal was to determine if patients tolerate generic Sandoz-Travoprost as well as brand Travatan Z, using a questionnaire.

3. Methodology

a. Study Design

Randomized controlled clinical trial, unblinded, crossover trial.

The crossover design was chosen to achieve the power required all the while limiting the number of patients required.

This study was not blinded to reproduce as much as possible the real situation experienced in clinic by the patients and the doctors. The use of masked bottles by the pharmacy was considered. However, some studies have suggested that the different characteristics of drop bottles may have an impact on the size of the drop or the concentration of the drug after 30 days[14]. So it was decided to use the original bottles.

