Cardiovascular: angina pectoris (1% to 5%), bradycardia (1% to 5%), chest pain (1% to 5%), hypertension (1% to 5%), hypotension (1% to 5%)

Central nervous system: Anxiety (1% to 5%), depression (1% to 5%), headache (1% to 5%), pain (1% to 5%)

Dermatological: hyperpigmentation of eyelashes, increased growth of eyelashes

Endocrine and metabolic: hypercholesterolemia (1% to 5%)

Gastrointestinal: dyspepsia (1% to 5%), gastrointestinal disorders (1% to 5%)

Genitourinary: prostate disease (1% to 5%), urinary incontinence (1% to 5%), urinary tract infection (1% to 5%)

Hypersensitivity: Hypersensitivity Reactions (1% to 5%)

Infection: Infection (1% to 5%)

Neuromuscular and skeletal: arthritis (1% to 5%), back pain (1% to 5%)

Respiratory: Bronchitis (1% to 5%), flu-like symptoms (1% to 5%), sinusitis (1% to 5%)

Post-marketing and / or case reports :

Asthma, tachycardia

vi. Contraindications

Allergy to prostaglandin analogues or any of the other ingredients of the product

Being pregnant or considering pregnancy (Risk Factor C for pregnancy)

vii. Interactions

Non-steroidal anti-inflammatory drug: may increase the therapeutic efficacy of prostaglandins

viii. Pharmacodynamics and pharmacokinetics

Start of action: 2 hours

Maximum effect: 12 hours

Half life: 45 minutes

ix. Inactivation and elimination

Inactivation by the kidneys, liver and lungs.

4. Study population

a. Target population:

All adult patients with primary open angle glaucoma, normotensive glaucoma, or ocular hypertension requiring pharmacological treatment seen at CHUS.

5. Sample size and inclusion / exclusion criteria

The calculation of the sample size is based on a paired t test, assuming a normal distribution of intraocular pressure. To demonstrate an equivalence between Travoprost original (Travatan Z) and generic Travoprost, a sample size of 69 patients will be required. This will detect a difference of 1.5mmHg with a power of 80% and an alpha of 0.05, assuming a standard deviation of 3.5mmHg. Assuming a loss at follow-up of 10%, the required number of patients is 76.

a. Inclusion criteria

- To be of age
- Be able to consent and sign the consent form
- Have a diagnosis of primary open angle glaucoma, normotensive glaucoma, or ocular hypertension requiring pharmacological treatment

b. Exclusion criteria

- Angle closure glaucoma
- Having had laser iridotomy
- Allergy known to Travatan or Travaprost, or to any other components of the products

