At the follow-up visit, if the patient qualifies for the study, resident [name] will present the study. If the patient agrees, resident [name] will complete the consent form with the patient and get his signature. The sociodemographic data of the patient will be collected and a complete ophthalmological examination will be performed. This examination will include visual acuity, external examination, evaluation of the cornea, anterior chamber, iris, lens, anterior vitreous, retina and optic nerve (with pharmacological dilatation). Intraocular pressure, gonioscopy, pachymetry and visual field Humphrey SITA Standard 24-2. Gonioscopy, pachymetry and the visual field could be delayed if they were done in the previous 4 months. The patient will receive a bottle of original Travoprost (Travatan Z) or generic Travoprost according to the prior randomization. The patient will receive explanations on how to put the drops.

During the second visit, at 3 weeks +/- 3 days, the IOP will be taken by resident [name] at the same time as the first visit +/- 1h. A bottle of the other medicine will be given to him.

At the third visit at 6 weeks +/- 3 days, the IOP will be taken by resident [name] at the same time as the first visit +/- 1h. The patient will have finished the study and a prescription of his starting medication will be given.

A questionnaire on tolerance and comfort of drops will be completed with the patient at the second and third visit.

c. For patients who drop out of the study or who are lost to follow-up:

A loss of follow-up of 10% is anticipated so the sample size has been increased by 10%.

d. Management of adverse effects:

The adverse effects of these drugs are well known and are mostly minor and transient. A questionnaire on tolerance and comfort of drops will be completed with the patient at the second and third visit. If, however, a patient is very concerned about an adverse reaction, they may contact the ophthalmology outpatient clinic or contact the resident on call.

Table: Summary of 3 visits by group

	Recruitment day (day 0)	Second visit (at 3 weeks)	Third visit (at 6 weeks)

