
Group 4 (Patient already randomized to receive generic Travoprost first)
	
 • Presentation of the study to the patient • Obtaining consent • A bottle of generic Travoprost given with instruction to instill a drop at bedtime in the eye reaches 	
 • IOP taken by the resident • Complete the questionnaire on the comfort of the treatment • A bottle of Travoprost original (Travatan Z) given with instructions to instill a drop at bedtime in the eye reaches 	
 • IOP taken by the resident • Complete the questionnaire on the comfort of the treatment • End of the study

9. Data analysis

The database will be created with Microsoft Excel.

Statistical calculations will be done with SPSS v20.

a. Comparison of the composition of the different groups

A t-test will be used for continuous variables (if the data are not normally distributed, a Mann-Whitney test will be used).

A Chi-square test will be used for categorical variables (if the frequency is less than 5 for a variable, an exact Fisher test will be used).

b. Comparison of groups at the end of the study

A paired t test will be used if the data is normally distributed (otherwise, a Wilcoxon test will be used).

c. Analysis of the therapeutic effect of drugs

An ANOVA test will be used to compare the effect of the treatments over time (an appropriate transformation will be applied to the data if it is not normally distributed).

d. Comparison of adverse effects between the two treatments

A McNeman test will be used to see if each side effect is as common with both treatments.

e. Comparison of compliance with each treatment

A paired t test will be used to see if patients have the same compliance for each treatment (Wilcoxon test if non-normal data).

10. Limitations

There is a potential bias of information if a patient believes that the generic is less effective, which could lead to a decrease in compliance or a change in dosage by the patient (eg: he could put it twice a day and not once). To counter this bias, the importance of abiding by the prescribed posology will be explained to patients.

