To avoid a learning bias, patients who start topical treatment for the first time will be told how to instill the drops during the initial outpatient visit. This instruction will be given by the resident to show the correct way to instill eye drops. A practice will then be performed using a new bottle of artificial tears. For those who are already taking Travoprost (Travatan Z) or generic Travoprost, they will be asked, during their first outpatient visit, to demonstrate how they instill their gout using a new bottle of artificial tears. If necessary, they will receive a short lesson given by the resident.

The loss to follow-up, inevitable in a prospective study, would lead to an information bias. The sample size has therefore been increased by 10%.

11. Ethical considerations

Adverse effects related to the use of Travoprost, as well as the patient's required time and movement, are the only real disadvantages. Follow-up will be provided by the treating team.

12. Anticipated benefits

With the information obtained as to the equal or lesser effectiveness of generic Travoprost compared to the original Travoprost (Travatan Z), we will be able to better inform patients asking if the generic version of their ophthalmic drop is equivalent reference drug. If we find equal efficiency, the savings could be remarkable. However, if we find less efficiency, then we

can ensure that the Travoprost served to our patients is the original Travoprost (Travatan Z) and not a generic, ensuring better control of IOP and therefore better control of the disease.

13. Dissemination of results

We hope to publish the results of this study in a specialized journal in ophthalmology and present them at local, national and international conferences. The results could also be communicated to pharmacists, to raise awareness of the effectiveness (or lack of effectiveness) of generic Travoprost.

14. Schedule

2015/08 Submission to the Scientific and Ethics Committees

2016/07 Start of patient recruitment

2017/07 Data analysis

2017/10 Writing and publication of the article

15. Budget

The cost of the study will be solely due to the ophthalmic drops delivered to patients.

Sample size:	69
Loss to follow-up:	10%
Increased sample size to compensate for anticipated loss to follow-up:	76
Cost per bottle of generic Travoprost (5mL):	\$44.99
Cost of generic Travoprost with taxes	\$51.74
Bottles of generic Travoprost per patient	1
Total per patient (including taxes):	\$51.74

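### The 69 patients and 80% power in section 5 do not fit the stated paired t-test inputs and the equivalence aim together

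*Combined protocol and SAP*

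**What the plan says.** Section 5 names the method: "The calculation of the sample size is based on a paired t test, assuming a normal distribution of intraocular pressure". It then gives the aim and the size: "To demonstrate an equivalence between Travoprost original (Travatan Z) and generic Travoprost, a sample size of 69 patients will be required". The next sentence describes the power differently, as power to find a difference: "This will detect a difference of 1.5mmHg with a power of 80% and an alpha of 0.05, assuming a standard deviation of 3.5mmHg". The paragraph ends with the allowance for loss: "Assuming a loss at follow-up of 10%, the required number of patients is 76".

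The paragraph does not say:
- whether 3.5 mmHg is the SD of within-patient differences or of single pressure readings;
- what within-patient correlation was assumed, if the latter;
- whether alpha is one- or two-sided;
- whether 1.5 mmHg is a margin or a difference to be found.

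Section 2 states the aim as "The primary goal was to determine if generic Sandoz-Travoprost is as effective as brand Travatan Z in lowering intraocular pressure". Section 12 contemplates only that the generic is equally or less effective. For the end-of-study comparison, section 9b says "A paired t test will be used if the data is normally distributed", with a Wilcoxon test otherwise. Section 9 names no test against a margin.

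**The concern.** The 80% is the plan's only statement of how well the trial can answer its main question. Power to find a difference of 1.5 mmHg is not power to show that the products lie within 1.5 mmHg of each other, and the two can differ widely at the same sample size. A paired t test also depends on the SD of the differences, and the only SD given is unlabelled.

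If the 80% belongs to another test, or to an SD other than the one a paired test uses, a reader cannot judge a result that fails to show equivalence. It could come from a small chance of success or from a real difference between the products. Section 12 intends to act on a finding of equal efficacy, so this matters.

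**Working it through.** **Inputs from section 5:** difference or margin δ = 1.5 mmHg, SD 3.5 mmHg, alpha 0.05, target power 80%, n = 69, loss 10%, enrolment 76.

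**Assumptions added here:** for TOST and non-inferiority, the margin is 1.5 mmHg and the true difference is 0. The within-patient correlation ρ is varied.

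**Formulas.** If 3.5 is the SD of a single reading, the SD of the differences is σd = 3.5 × √(2(1 − ρ)). This equals 4.95 at ρ = 0 and 3.5 at ρ = 0.5. Paired t-test power comes from the noncentral t distribution with n − 1 degrees of freedom and noncentrality δ√n/σd. The normal approximation to the size is n = ((zα + zβ)σd/δ)². TOST power is the probability that both one-sided tests reject, integrated over the distribution of the sample SD. At n = 68, 200,000 simulations gave 0.591, 0.810 and 0.937 for ρ = 0, 0.3 and 0.5, which agrees with the table below.

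**1. Reproducing 69.** Take 3.5 as the single-reading SD, ρ = 0 and a one-sided 5% test. The approximation is ((1.645 + 0.842) × 4.95/1.5)² ≈ 67.3, so 68. The exact t calculation gives 69 (80.2%; 68 gives 79.6%). This is also the calculation for one-sided non-inferiority with margin 1.5 and true difference 0. The number 69 is therefore not a computing slip.

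**2. A second route to 69.** A two-sided 5% test with ρ = 0.22 has σd = 3.5 × √1.56 ≈ 4.37, and 69 pairs give 80.2%.

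**3. The literal paired reading.** With σd = 3.5 and a two-sided test, the approximation is ((1.960 + 0.842) × 3.5/1.5)² ≈ 42.7, so 43. The exact calculation gives 45 (80.3%; 44 gives 79.4%). Other tests at σd = 3.5 need 36 (one-sided), 49 (TOST, 5% per side) or 60 (TOST, 2.5% per side). None is 69.

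**4. Equivalence power at n = 69 on each reading**

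| Reading | t-test power | TOST, 5% per side |
|---|---|---|
| σd = 3.5, two-sided | 93.9% | 94.0% |
| Single-reading SD 3.5, ρ = 0, one-sided | 80.2% | 60.3% |
| Single-reading SD 3.5, ρ = 0.22, two-sided | 80.2% | 76.1% |

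**5. Where 69 and 80% for equivalence do agree.** With 3.5 as the single-reading SD, TOST needs exactly 69 at ρ of about 0.28 (5% per side) or about 0.42 (2.5% per side). The plan states neither the test nor such a correlation.

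**6. Loss to follow-up.** 69 × 1.10 = 75.9, hence 76. But 76 × 0.90 = 68.4 evaluable, and 69/0.90 = 76.7 would round up to 77. The gap is under one patient, or about half a point of t-test power.

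**7. Power at 68 evaluable, single-reading SD 3.5**

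| ρ | One-sided t or non-inferiority, 5% | Two-sided t, 5% (as non-inferiority, 2.5%) | TOST, 5% per side | TOST, 2.5% per side |
|---|---|---|---|---|
| 0 | 79.6% | 69.3% | 59.3% | 38.5% |
| 0.2 | 86.9% | 78.6% | 73.8% | 57.3% |
| 0.3 | 90.5% | 83.7% | 81.0% | 67.5% |
| 0.5 (σd = 3.5) | 96.8% | 93.6% | 93.6% | 87.2% |
| 0.6 | 98.8% | 97.3% | 97.7% | 94.7% |
| ρ needed for 80% | 0.01 | 0.23 | 0.29 | 0.42 |

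**The case against.** The best defence is that section 5 is incomplete rather than contradictory. The number 69 is returned exactly by a one-sided test with 3.5 as the single-reading SD. The reference to normally distributed intraocular pressure suggests that 3.5 does describe readings. Sections 2 and 12 can be read as a non-inferiority aim, for which 69 and 80% agree. The 60% and 76% belong to TOST, which the plan does not contain. Zero correlation is an unfavourable case for two readings on the same patient at a matched time of day. TOST itself reaches 80% at 69 with a correlation near 0.28.

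Much of this is right. 69 can be reproduced, and no shortfall is shown. The lack of any equivalence test in section 9 is a related problem that explains part of the mismatch.

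It does not rescue the statement as written. Section 5 says equivalence, not non-inferiority. The one-sided reading needs unstated assumptions, and it takes no credit for within-patient correlation in a crossover that section 3a says was chosen to reach the required power with fewer patients. The dropout objection also stands: the 10% increase is openly described and its effect is trivial. The conclusion does not depend on it.

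**Conclusion.** The concern holds. The size, power, test and aim in section 5 do not fit together. On the literal paired reading, 80% is too low: 45 pairs would do, and 69 give about 94%. On the t-test readings that return 69, the 80% belongs to a difference or non-inferiority test, and the matching equivalence power is about 60% or 76%.

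The TOST figures rest on a margin of 1.5 mmHg and a true difference of 0. The 60% and 76% also use 5% per side and 3.5 mmHg as the single-reading SD. They are conditional values, not bounds. Whether the trial is under- or overpowered cannot be settled from the documents, because actual power depends on a within-patient correlation that they do not give. The paragraph should be corrected; the finding gives no ground for enrolling more patients.

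**What to change.** Rewrite the sample-size paragraph in section 5 and leave enrolment as it is.

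1. From the source of the 3.5 mmHg, say whether it is the SD of within-patient differences or of single readings. If single readings, give the assumed correlation. Take both from that source, not from the trial's own data.
2. Give 1.5 mmHg one role (equivalence margin, non-inferiority margin or difference to detect), with the matching one- or two-sided alpha. If it is not an equivalence margin, replace the word equivalence in section 5.
3. Replace the 80% with the power that about 68 evaluable patients give for that choice.
4. If the source cannot be recovered, print power conditional on correlation, test and alpha, as in the last table of the working, not as a fixed range.
5. State that 76 enrolled with 10% loss leaves about 68 evaluable.

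The cost is the rewording of one paragraph, with no extra patients, visits or money. The authors must commit to one meaning for the 1.5 mmHg, and the stated power may become less favourable than 80%.

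### The 10% loss allowance multiplies 69 by 1.1 instead of dividing by 0.90, so 76 enrolled gives an expected 68.4 evaluable patients, 0.6 below the stated 69

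*Combined protocol and SAP*

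**What the plan says.** Section 5 bases the calculation on a paired t test and concludes that "a sample size of 69 patients will be required". The stated inputs are: "This will detect a difference of 1.5mmHg" "with a power of 80% and an alpha of 0.05", with an SD of 3.5 mmHg. It then makes the allowance for loss: "Assuming a loss at follow-up of 10%, the required number of patients is 76".

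Section 8c gives the method: "A loss of follow-up of 10% is anticipated so the sample size has been increased by 10" per cent. Section 10 repeats it: "The sample size has therefore been increased by 10" per cent.

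The section 15 budget lists 69, 10% and 76, the last under the label "Increased sample size to compensate for anticipated loss to follow-up". It costs one bottle of generic per patient at $51.74 with taxes and gives a total of $3,926.95, against a research award of $4,000.

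**The concern.** An allowance for loss should leave the required number after the loss has occurred. The 10% is lost from those enrolled, not from the 69 who are needed, so the enrolled number N must satisfy N x 0.90 >= 69. Adding 10% to 69 answers a different question and always gives a slightly smaller number.

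The documents describe nothing that would close the gap. No replacement of dropouts is mentioned. The paired t test needs the pressure reading from both the 3-week and the 6-week visit, so a patient lost before the third visit contributes no paired difference.

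At stake is the enrolment target, which falls just short of the plan's own requirement under the plan's own loss rate. It is stated in two sections and its method in two more.

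**Working it through.** **Inputs.** Required evaluable 69, loss 10%, target 76, difference 1.5 mmHg, alpha 0.05, power 80%, SD 3.5 mmHg (all section 5). Increase of 10% (sections 8c and 10). Bottle price $44.99, or $51.74 with taxes, generic total $3,926.95, award $4,000 (section 15). Section 5 does not say whether the test is one- or two-sided, or whether 3.5 mmHg is the SD of a single reading or of the within-patient difference.

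**1. Reproduce the plan's figure.** 69 x 1.10 = 75.9, rounded to 76. The budget confirms this route:
- $51.74 / $44.99 is a factor of 1.15, and $44.99 x 1.15 = $51.7385.
- 75.9 x $51.7385 = $3,926.95, the stated total.
- 76 x $51.74 would be $3,932.24.

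The unrounded 75.9 was therefore carried into the cost.

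**2. Apply the allowance to those enrolled.** N = 69 / (1 - 0.10) = 76.67, rounded up to 77.

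**3. Expected evaluable patients at 10% loss.**
- 76 x 0.90 = 68.4, which is 0.6 below 69.
- 77 x 0.90 = 69.3.

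With 76 enrolled, 69 remain only if at most 7 are lost, and 7/76 = 9.2%.

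**4. Chance of keeping 69.** Assume each patient is lost independently with probability 10%. The probability of at least 69 evaluable is then 0.505 with 76 enrolled and 0.637 with 77. With 76, the median number evaluable is 69.

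**5. Effect on power.** Paired t test, difference 1.5 mmHg, alpha 0.05, noncentrality 1.5 x sqrt(n) / SD of the difference:

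| Reading of the SD and the test | n = 68 | n = 69 |
|---|---|---|
| SD of difference 3.5, two-sided | 93.6% | 93.9% |
| SD of difference 4.38, two-sided (assumed; back-solved so that 69 gives about 80%) | 79.5% | 80.1% |
| SD of difference 3.5 x sqrt(2) = 4.95, one-sided (assumed; no correlation within patient) | 79.6% | 80.2% |

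The cost of one patient is about 0.3 to 0.6 percentage points in each row.

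**6. Cost of 77.** 77 x $51.74 = $3,983.98, which is $16.02 below the award.

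**The case against.** The strongest reply is that nothing practical follows. 76 is correctly computed from the rule that the plan states openly, and the four sections agree on the figures and the rule. The 10% is a round planning value with no source given, and a 9% loss would remove the gap. If 3.5 mmHg is the SD of the difference, 80% two-sided power needs only about 45 patients, so 76 leaves a wide surplus. All of this stands as an argument about size. It does not make 1.1 the right factor: the plan chose 10%, and at 10% its target falls short on average.

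A reader might infer that 76 patients cannot yield 69 evaluable. The documents do not support that. Under independent 10% loss the median is 69, and the chance of reaching 69 is about even. Only the mean falls short, by 0.6 of a patient.

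A reader might also infer that the trial is underpowered because of this step. That is not supported either. Power falls below 80% only under assumed inputs for which 69 was already on the boundary, and then by about half a point.

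A further objection is that correcting 76 lends weight to a 69 that has not been justified. This is fair. With the stated inputs and 3.5 mmHg as the SD of the difference, the two-sided requirement is 43 (normal approximation) or 45 (t). The 69 is reached only under assumptions the plan does not state, such as the one-sided row in the table. Whether 69 is adequate for showing equivalence is a separate question. This point takes 69 as given.

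**Conclusion.** The point holds and is minor. The loss allowance uses the wrong factor: 1.1 gives 76, whereas dividing by 0.90 gives 77. At the plan's own 10% loss, 76 enrolled gives an expected 68.4 evaluable patients against the stated 69, and power changes by about 0.3 to 0.6 points.

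The enrolment shortfall rests only on the plan's 69 and 10%. The probabilities also assume independent losses. The power figures depend on how the SD and the sidedness are read, which section 5 leaves open. The conclusion is limited to a misstated enrolment target and says nothing about whether 69 itself is right.

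**What to change.** Restate the figure in one of two ways.

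- **Keep 76.** State in section 5 that about 68 evaluable patients are expected after 10% loss. Give the power for that number, saying which SD and which sidedness it uses. This needs wording only.
- **Use 77.** Write 77 (69 / 0.90) in section 5. Change the sentences in sections 8c and 10 that describe a 10% increase, since they would otherwise contradict section 5. In section 15, change the inflated sample size to 77 and the total to $3,983.98. This costs one more patient and one more bottle of generic, and stays within the $4,000 award.

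Under either option, correct the budget total of $3,926.95, which matches 75.9 patients; for 76 it is $3,932.24. If 69 is recalculated, divide the new number by 0.90 and carry the result through the same sections.
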